2.1 Research background, project objectives and the foundation of previous research

2.1.1 Research background

Cancer has become a major social, economic and public health issue in the 21st century and is one of the leading causes of death worldwide. In 2020, both the number of new cancer cases and deaths in China ranked first in the world. With the rapid development of medical technology, early diagnosis of tumors is of vital importance for improving the survival rate and quality of life of patients. However, existing tumor diagnostic methods, such as imaging examinations, histopathological examinations, and traditional tumor marker detection, still have deficiencies in terms of sensitivity,

specificity, and early detection capabilities. They cannot achieve the detection of multiple tumors with a single method, and may have limitations such as high professional requirements, long time consumption, and high detection costs. Therefore, it is of vital importance to develop a novel pan-tumor screening and diagnosis method that is low-cost, highly sensitive and highly specific.

Free nucleosomes in cells are nucleosomes released into circulating tissues after apoptosis or necrosis of cells, and they retain some specific information of the origin cells and tissues. The histone modification status on the free nucleosomes produced by tumor cells reflects the metabolic state and epigenetic changes of tumor cells. Therefore, histone modification of free nucleosomes in cells is expected to become a new biomarker for non-invasive tumor detection. Although previous studies have found the association between histone succinylation modification and tumors, and free nucleosomes in cells retain specific histone modifications of the origin tumor cells, histone succinylation modification of free nucleosomes in cells has not yet been applied to tumor screening and detection. Therefore, it is urgently necessary to study whether histone succinylation modification of free nucleosomes can be used as a low-cost, highly sensitive and highly specific pan-tumor marker and applied in the early screening, therapeutic effect evaluation and prognosis of tumors.

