Succinylation modification, as a widely existing post-translational modification of proteins, has potential biomarker value in malignant solid tumors. Besides tumors, existing studies have shown that some diseases (such as inflammatory diseases, infectious diseases, metabolic diseases, cardiovascular diseases, neuro-psychological diseases, etc.) have certain correlations with non-histone succinylation modification. The role of histone succinylation modification in other diseases is currently lacking in relevant clinical research evidence and awaits further exploration in this study. Therefore, this research focuses on malignant solid tumors, not only filling the knowledge gap in this field but also laying the foundation for future expansion to other diseases.

2.1.2 project objective

The core objective of the project is to systematically verify and establish the clinical

application value of serum histone succinylation modification as a novel, efficient and non-invasive pan-tumor biomarker.

Objective 1: Verify the potential of pan-tumor screening: Through large-scale case-control studies, it is clearly confirmed that there are significant differences in histone succinylation levels in serum between patients with malignant solid tumors and healthy individuals, thereby providing a solid evidence-based basis for developing it into a blood-based early screening tool suitable for multiple tumor types.

Objective 2: Exploring clinical application scenarios: The project will conduct an in-depth analysis of the association between serum histone succinylation levels and different types of tumors as well as different tumor stages, and evaluate its ability to distinguish tumor types and reflect disease progression. Meanwhile, analyze its correlation with therapeutic effects (changes in levels before and after surgery, radiotherapy, and systemic treatment) and clinicopathological characteristics, and explore its application prospects in dynamic monitoring of therapeutic effects and prognosis assessment.

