2.2 Risk/Benefit assessment

risk assessment:

This study was an observational one, and the core intervention was only a single venous blood sample collection of 3mL (approximately 1ml of serum). This operation

is a routine and mature medical practice in clinical practice, with extremely low and controllable risks.

Benefit evaluation:

Cancer patients: They will not receive immediate individualized diagnosis or treatment recommendations from this study. However, the data it contributes will drive the development of better tumor markers, which may benefit its future disease management (such as more precise follow-up monitoring).

Healthy control subjects: Contribute to establishing baseline standard values for healthy populations and promote public health. After the research is completed and the method is mature, the baseline data in which it participated may provide a reference background for its own future similar screening.

三、 Research objectives and endpoints

3.1 objective

3.1.1 main purpose

To evaluate the differences in serum histone succinylation between malignant solid tumors and healthy individuals, in order to verify its early screening value.

3.1.2 secondary objective

To clarify the correlation between histone succinylation modification in serum and different types of tumors and tumor stages, and to statistically analyze the correlation between histone succinylation in serum and therapeutic effects (including surgical treatment, radiotherapy, and systemic therapy) as well as clinicopathology.

3.2 evaluation index

The evaluation indicators are: the sensitivity, specificity, positive predictive value, negative predictive value of the serum histone succinylation screening method, and the predictive value of the Youden index (early diagnosis, therapeutic effect evaluation and prognosis).

四、 study population

4.1 inclusion criteria

case group

- 1) ≥ 18 years old, gender not limited;
- 2) Malignant solid tumors diagnosed by cytology or histology require subsequent anti-tumor treatment (systemic therapy, radical or concurrent chemoradiotherapy/radiotherapy, or surgical treatment).

control group

- 1) ≥ 18 years old, gender not limited;
- 2) Non-tumor patients undergoing health check-ups;

4.2 exclusion criteria

- 1) Pregnant women
- 2) Those with severe mental disorders or language communication disorders;
- 3) Other circumstances where the researcher deems it unsuitable to participate in this study.

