5.2.2 Research flowchart

5.2.3 Blood collection process table

grouping								
	Screening period							
healthy person	D-7—D0							
Cancer patients are receiving systemic treatment		Chemotherapy cycle						
		C1D1	C2	C3	C4	C5	C6	
	D-7—D0			D1± 3		D1±3		
Cancer patients who receive radical chemoradiotherapy/radiotherapy	D-7—D0	After the completion of radiotherapy/chemoradiotherapy		Four to six weeks after the completion of radiotherapy/chemoradiotherapy				
		D _{end} D _{end} +3		On the day of follow-up				
A tumor patient undergoing surgery	D-7—D0	postoperation	Postoperative discharge day/the day before discharge					
	D1—D3							

5.3 statistic analysis

This study adopted a mismatched case-control study (500 cases in the case group and 500 cases in the healthy control group). The sample size was determined based on the effect size of the previous pre-experiment (Cohen's $d=1.2$) and considering a 10% dropout rate. All statistical analyses were performed using R, with a test level of $\alpha=0.05$. Main analysis 1) Comparison of histone succinylation levels between groups - After Shapiro-Wilk normality and Levene homogeneity of variance tests, independent sample t-tests (conforming to normal distribution) or Mann-Whitney U tests (non-normal data) were selected. Report mean difference (MD)/median difference and 95% confidence interval (CI), Cohen's d effect size; 2) Diagnostic

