efficacy evaluation - Calculate the area under the curve (AUC) and its Bootstrap 95% CI through the ROC curve, and determine the optimal cut-off value by maximizing the Youden index. And calculate the sensitivity, specificity, positive predictive value (PPV), negative predictive value (NPV), and their exact Clopper-Pearson 95% CI. Secondary analysis: 1) Subgroup correlation - One-way analysis of variance (ANOVA) or Kruskal-Wallis test was used to compare the level differences among different tumor types (Bonferroni-adjusted post hoc test), and Cuzick's trend test was used to analyze the ordered association of TNM stages; 2) Therapeutic effect evaluation - The level changes before and after treatment were evaluated using paired t-test /Wilcoxon signed-rank test; 3) Prognostic value - The baseline succinylation level (median grouping) was included in the Cox proportional hazards model. After adjusting for age, stage, and treatment regimen, the hazard ratio (HR) and 95% confidence interval (CI) were calculated. The survival curve was plotted using the Kaplan-Meier method (Log-rank test). Multivariate analysis: A Logistic regression model was constructed (including succinylation level and covariates such as age and gender). AUC was compared by DeLong test, goodness-of-fit was evaluated by Hosmer-Lemeshow calibration curve, and clinical net benefit was analyzed by decision curve (DCA). If multi-site modifications are detected, LASSO regression is used to screen biomarker combinations. Quality control: Grubbs test /Winsorize for outliers, multiple imputation (MICE) for filling <5% of missing covariates. Sensitivity analysis: Robustness was verified by excluding stage I tumors, and the 70%-30% dataset was split for cutoff value training - validation. All multiple comparisons were controlled for the false discovery rate (FDR) using the Benjamini-Hochberg method.

六、Ethical requirements

Clinical research will comply with relevant regulations such as the Declaration of Helsinki of the World Medical Congress. The research can only be implemented after it has been approved by the ethics committee before it commences.

Before each subject is enrolled in this study, the researcher is responsible for providing the subject or their agent with a complete and comprehensive introduction

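### The main analysis chooses its only cut-off by the Youden index, so specificity is left uncontrolled although the stated main purpose is to verify early screening value

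*Protocol*

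**What the plan says.** In Protocol 5.3 the second part of the main analysis builds a ROC curve, reports the AUC with a bootstrap interval, and then instructs the analyst to "determine the optimal cut-off value by maximizing the Youden index". Sensitivity, specificity, PPV and NPV with exact intervals follow. No other cut-off and no minimum specificity is named. Section 3.2 also lists the Youden index among the evaluation indicators.

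The purpose is stated in several places. Section 3.1.1 compares patients and healthy people "in order to verify its early screening value", and Phase Three in 5.2.1 repeats that aim. Objective 1 in 2.1.2 looks towards "developing it into a blood-based early screening tool suitable for multiple tumor types". Section 2.1.1 sees a need to "develop a novel pan-tumor screening and diagnosis method that is low-cost, highly sensitive and highly specific".

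Two further items in 5.3 touch on cut-offs. A 70/30 split trains and then validates the cut-off, as a sensitivity analysis. A decision curve is attached to the multivariate logistic model.

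**The concern.** The Youden index is sensitivity + specificity - 1. Maximising it trades one point of sensitivity for one point of specificity at par, whatever the prevalence. In terms of people screened, that implies a missed cancer counts as (1 - p)/p false positives, where p is the prevalence. At an assumed p of 1% the ratio is 99. The protocol neither states nor defends such a weighting.

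This is a matter of the criterion, not of sampling error. It would remain in an infinite sample, and the 70/30 split does not touch it, because the split validates a cut-off chosen by the same rule. The risk is that the trial reports a balanced pair of accuracy figures as its main diagnostic result, while the sensitivity that remains once false positives are held low has no pre-specified estimate or interval.

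**Working it through.** **Inputs from the documents.** Effect size and attrition: "effect size of the previous pre-experiment (Cohen's $d=1.2$) and considering a 10% dropout rate". Group sizes: "500 cases in the case group and 500 cases in the healthy control group". Both are in Protocol 5.3. The protocol states no expected sensitivity, specificity or false-positive rate, so there is no accuracy figure to reproduce. Its one derived figure, 500 per group, does not follow from d = 1.2: two-sided at 5%, even 99.9% power needs 36 per group, or 40 after 10% dropout. That is a separate matter; only d is used below.

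**Assumptions.** Controls N(0, 1), cases N(mu, r²), where r is the case/control SD ratio. Holding d at 1.2 on the average-variance SD gives mu = 1.2 × sqrt((1 + r²)/2). Prevalences are assumed, because the protocol gives none.

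**Step 1: equal SDs (r = 1).** The Youden maximum lies where the two densities cross, at c = d/2 = 0.60.
- Specificity = sensitivity = Phi(0.60) = 72.6%; J = 0.451.
- False-positive rate = 1 - Phi(0.60) = 27.4%.
- AUC = Phi(1.2/sqrt(2)) = 0.802.
- Varying d alone: 1 - Phi(0.4) = 34.5% at d = 0.8 and 1 - Phi(0.8) = 21.2% at d = 1.6.

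**Step 2: fixed specificity, equal SDs.** Sensitivity = 1 - Phi(z - 1.2), where z is the normal quantile of the chosen specificity.
- At 95%: 1 - Phi(1.645 - 1.2) = 32.8%.
- At 99%: 1 - Phi(2.326 - 1.2) = 13.0%.

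**Step 3: unequal SDs.** The Youden maximum was found numerically. Sensitivity at 95% specificity is 1 - Phi((1.645 - mu)/r).

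| r | mu | Youden false-positive rate | Youden sensitivity | Sensitivity at 95% specificity |
|---|---|---|---|---|
| 0.5 | 0.949 | 36.8% | 89.0% | 8% |
| 1 | 1.200 | 27.4% | 72.6% | 33% |
| 1.5 | 1.530 | 16.5% | 64.5% | 47% |
| 2 | 1.897 | 11.0% | 63.2% | 55% |
| 3 | 2.683 | 6.3% | 65.0% | 64% |

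The same d is thus compatible with a Youden false-positive rate anywhere from about 6% to 37%.

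**Step 4: what this means per cancer found, at an assumed 1% prevalence.** False positives per true positive = (1 - spec)(1 - p)/(sens × p).
- Youden, r = 1: 0.274 × 0.99/(0.726 × 0.01) = 37, PPV 2.6%.
- 95% specificity, r = 1: 0.05 × 0.99/(0.328 × 0.01) = 15, PPV 6.2%.
- Youden, r = 3: 0.063 × 0.99/(0.650 × 0.01) = 9.6, PPV about 9%.

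**Step 5: behaviour with 500 + 500 (4000 simulated trials, r = 1).**
- At the empirical Youden cut-off the true false-positive rate averages 28.1%, with a 95% range of 18.6% to 38.3%.
- At the empirical 95th control percentile, sensitivity averages 0.331 with SD 0.039, so about ±1.96 × 3.9 = ±7.6 points; the realised false-positive rate averages 5.1%.
- The 99th percentile rests on about 0.01 × 500 = 5 controls. The realised false-positive rate then has a 95% range of about 0.45% to 2.3%, and sensitivity one of 7.6% to 21.8%.

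**The case against.** Several things can fairly be said for the plan.

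- **Youden is a legitimate and customary choice.** It yields a defined cut-off with exact intervals, and 5.3 agrees with 3.2. A reader might infer that the plan produces no operating point at all. It does produce one; the difficulty is that it was not chosen with screening in mind.
- **The background asks for both properties.** Section 2.1.1 wants high sensitivity as well as high specificity, and mentions diagnosis as well as screening. A reader might infer that the protocol's own text puts specificity first. It does not. The case for a controlled specificity comes from the screening purpose, not from a stated ranking.
- **The ROC curve will exist.** Sensitivity at any specificity can be read from it, so it would be too strong to say that the figure can never be obtained. What is missing is a named point, fixed in advance, with an interval.
- **The 27% is conditional.** It needs normal data with equal SDs, whereas 5.3 itself plans tests of both and a rank-based alternative. Cases pool many tumour types and stages, so unequal spread is plausible. At r = 3 the Youden and 95%-specificity points nearly coincide. This stands, and is why a range is given.
- **Extra operating points could sit in a statistical analysis plan.** That would settle the matter if the protocol were silent. It is not: it fixes the rule in the main analysis and presents the result as the best cut-off.

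The decision curve weighs false positives against detected cancers, but it belongs to the logistic model, does not set the cut-off and has no stated threshold range.

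**Conclusion.** The point holds as one of matching the cut-off rule to the purpose. The main analysis fixes a single rule that leaves specificity uncontrolled, while 3.1.1 says the study is to verify early screening value. At d = 1.2 the false-positive rate at that cut-off would be about 27% under normality with equal SDs, and about 37% to 6% for SD ratios of 0.5 to 3. The direction does not hang on the 27%: even at the favourable end, at an assumed 1% prevalence, there are nearly ten false positives per cancer found.

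Two stronger readings are not supported. The 27% is not a property of the assay or a figure from the protocol; it follows from a model for the pilot effect. Nor do the documents give grounds for dropping Youden or for making 99% specificity a main result, which 500 controls would support only poorly. Moving the cut-off does not improve the marker; it shows what the marker can detect when false positives are limited.

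**What to change.** In Protocol 3.2 and in the diagnostic part of the main analysis in 5.3:

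- Add as a main diagnostic result the sensitivity at one high specificity fixed before the data are seen, for example 95% or another level that the sponsor justifies.
- Take the cut-off as the corresponding percentile of the controls.
- Give a bootstrap 95% CI that re-estimates the cut-off in every resample, so that uncertainty in the threshold is carried through.
- Keep the Youden cut-off and its accuracy figures alongside.
- If 99% specificity is of interest, report it as exploratory.

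The cost is a wording change and a few lines of R, using samples already planned. The downside is a less favourable and less precise headline: about 33% ± 8 points at 95% specificity with equal SDs, or about 47% to 64% for SD ratios of 1.5 to 3. If cases were less variable than controls it would be lower still (about 8% at a ratio of 0.5). The level has to be set in advance, because choosing it after seeing the ROC curve would again make the operating point data-driven.

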The control group was the same as the case group.

五、 study design

5.1 overall design

This study is a single-center prospective case-control study.

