5.2 Research design process

5.2.1 Study the specific implementation process

1. Phase One: Screening and enrolling the population

- i. Conduct ethical reviews and clinical research protocol reviews for the project;
- ii. It is planned to select 500 patients with malignant solid tumors, collect their basic information and sign the "Informed Consent Form".
- iii: It is planned to select 500 healthy subjects and collect basic information.

2. Phase Two: Collect blood samples for serum histone succinylation detection

[figure not shown]
Blood samples were collected from all 500 enrolled individuals and 500 healthy subjects who met the requirements for serum histone succinylation detection.

3. Phase Three: Statistical analysis of Screening Results

- i. Western blot was used to evaluate the differences in serum histone succinylation between malignant solid tumors and healthy individuals to verify its early screening value.

ii. Statistically analyze the correlation between serum histone succinylation and tumor efficacy (including surgical treatment, radiotherapy, and systemic therapy) as well as clinicopathology. The therapeutic effect was evaluated using RECIST1.1 criteria.

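### PPV and NPV of the screening method would come straight from a 500:500 case-control sample, so they describe a population in which half have cancer

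*Protocol*

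**What the plan says.** Section 5.1 defines the design: "This study is a single-center prospective case-control study". Section 5.3 gives the group sizes: "This study adopted a mismatched case-control study (500 cases in the case group and 500 cases in the healthy control group". Section 5.2.1 repeats them for blood sampling: "Blood samples were collected from all 500 enrolled individuals and 500 healthy subjects".

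Under section 4.1, cases are patients whose cancer is already confirmed ("Malignant solid tumors diagnosed by cytology or histology require subsequent anti-tumor treatment") and controls are "Non-tumor patients undergoing health check-ups".

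The evaluation indicators in section 3.2 include the "positive predictive value, negative predictive value of the serum histone succinylation screening method", and the main purpose in section 3.1.1 is to verify value for early screening. In section 5.3, diagnostic efficacy is the second part of the main analysis. The cut-off maximises the Youden index, and then: "And calculate the sensitivity, specificity, positive predictive value (PPV), negative predictive value (NPV), and their exact Clopper-Pearson 95% CI".

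The protocol nowhere gives a target-population prevalence or a re-weighting, and nowhere limits PPV and NPV to the 1:1 sample.

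**The concern.** PPV and NPV depend on how common the disease is among the people tested. Here that share is chosen by the investigators: 500/(500 + 500) = 50%. A proportion such as true positives over all positives then answers a question about a population in which every second person has cancer, which is not a screening population.

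The interval method rules out a more generous reading. Clopper-Pearson is an interval for a count over a count. A prevalence-adjusted PPV is a function of sensitivity, specificity and an outside prevalence, and this interval does not fit it.

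Both indices are named evaluation indicators and bear directly on the screening claim. A report that followed the plan would state a PPV far above what a screened person with a positive result would face. The word exact on its interval would suggest precision, although the interval covers sampling error only and takes no account of the prevalence.

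**Working it through.** **Inputs from the protocol.** 500 cases, 500 controls, Cohen's d = 1.2, 10% dropout, Youden cut-off (all section 5.3). The protocol states no PPV, NPV, sensitivity, specificity or prevalence, so there is no planned figure to reproduce.

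**Assumptions.** Equal-variance normal marker values, used only to turn d into sensitivity (Se) and specificity (Sp). Prevalences p from 0.5% to 20%, used only to show size.

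**Step 1: Se and Sp implied by d.** Under this model the Youden cut-off lies midway between the two means, so Se = Sp = Φ(d/2) = Φ(0.6) = 0.7257.

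**Step 2: what the plan would report.** Expected counts are TP = 363, FN = 137, TN = 363, FP = 137.
- PPV = 363/(363 + 137) = 72.6%
- NPV = 363/(363 + 137) = 72.6%
- Clopper-Pearson 95% interval for 363/500: 68.5% to 76.5%, for each

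**Step 3: the same test at other prevalences.**
- PPV = Se·p / [Se·p + (1 − Sp)(1 − p)]
- NPV = Sp(1 − p) / [Sp(1 − p) + (1 − Se)p]

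At p = 0.01, for example, PPV = 0.007257/(0.007257 + 0.2743 × 0.99) = 0.0260.

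The PPV intervals use the delta method on the log positive likelihood ratio, with the cut-off treated as fixed. LR+ = 0.7257/0.2743 = 2.646, and SE(log LR+) = √[0.2743/(500 × 0.7257) + 0.7257/(500 × 0.2743)] = 0.0778.

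| Prevalence | PPV | 95% interval for PPV | NPV |
|---|---|---|---|
| 50% (the sample) | 72.6% | 68.5–76.5% (planned) | 72.6% |
| 5% | 12.2% | 10.7–14.0% | 98.0% |
| 2% | 5.1% | 4.4–5.9% | 99.2% |
| 1% | 2.6% | 2.2–3.0% | 99.6% |
| 0.5% | 1.3% | 1.1–1.5% | 99.8% |

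At 1% the planned PPV is 72.6/2.6 ≈ 28 times too high, and there are about 37 false positives per true positive. None of the adjusted PPV intervals overlaps the planned one.

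**Step 4: does the result hang on the assumptions?**
- Higher prevalence: PPV is 22.7% at 10% and 39.8% at 20%, both well below 68.5%.
- Better test: with Se = Sp = 90% assumed, PPV is 90.0% in the sample (87.0% to 92.5%) and 8.3% at 1%.
- Cut-off chosen in the data: simulating 500 + 500 subjects at d = 1.2 and re-selecting the Youden cut-off each time gives a 95% range for PPV at 1% of about 2.1% to 3.7%. This is wider than 2.2–3.0%, but still nowhere near the planned interval.
- Dropout: if the whole 10% fell on one group, the case fraction would be 450/950 = 47.4% or 500/950 = 52.6%.
- The 70%-30% split: if it keeps the 1:1 mix, the validation part has the same fault.

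**Step 5: decision curve (secondary and conditional).** Section 5.3 also says "clinical net benefit was analyzed by decision curve (DCA", alongside the logistic model. If that model is fitted in the 1:1 sample and left uncorrected, its intercept and net benefit also carry the 50% case fraction. As an illustration, take succinylation as the only predictor and an assumed 10% threshold, with NB = Se·p − (1 − Sp)(1 − p)·0.1/0.9:
- In the sample, Se = 0.992 and 1 − Sp = 0.891, so NB = 0.447, against 0.444 for treat-all.
- At 1% prevalence the uncorrected model gives −0.088. After the intercept is shifted by ln(0.01/0.99) = −4.595, it gives +0.0003.

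**The case against.** The strongest reply is that little of the study is affected. The between-group comparison, AUC, sensitivity, specificity and cut-off all stand, and anyone can recompute PPV from the reported sensitivity and specificity. That is true, and the criticism is limited accordingly. It does not make the planned PPV and NPV right: they are named indicators of a screening method, and the protocol gives readers no warning.

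A second reply is that the protocol never says the proportions are unadjusted, and that an SAP could supply a prevalence. The reading is an inference, but a strong one. The protocol itself names the quantity, the sample and the interval method, and an SAP using Bayes' formula would have to depart from the stated interval.

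Third, the size rests on assumed prevalences and on a normal model, while section 5.3 allows for non-normal data. This stands. Only the direction is free of assumptions, although Step 4 shows that the gap stays large over a wide range.

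Fourth, the delta-method intervals are too narrow because the cut-off is selected in the same data. This also stands, and the fix allows for it.

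Finally, the decision-curve figures depend on a threshold, a prevalence and a one-predictor model that the protocol does not fix. They are illustrative, and the main conclusion does not need them.

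**Conclusion.** The plan is wrong as written on this point and should be corrected before analysis. Followed literally, it gives a PPV that is too high and an NPV that is too low for every screened population with less than 50% cancer. That direction needs only the 1:1 design and a test better than chance. The size needs more: with d = 1.2, equal-variance normal data and an assumed 1% prevalence, PPV is 72.6% as planned against 2.6%, and NPV 72.6% against 99.6%.

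The high adjusted NPV is not evidence of a good test either, because at 1% prevalence 99% of people are free of cancer before any testing. The adjusted values also rest on sensitivity measured in patients with an established diagnosis, which may not carry over to people being screened.

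**What to change.** In section 5.3, replace the PPV and NPV part of the sentence with wording such as:

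> Sensitivity and specificity will be reported with exact Clopper-Pearson 95% CIs. PPV and NPV will be calculated from them by Bayes' formula at stated and justified screening prevalences (for example 0.5%, 1%, 2% and 5%). Their 95% CIs will come from a bootstrap within cases and within controls that re-selects the cut-off in each resample. Raw proportions in the 1:1 sample will not be presented as screening performance. The adjusted values assume that sensitivity in already diagnosed cases carries over to screened people.

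A delta-method interval is a simpler alternative where the cut-off has been fixed beforehand in separate data.

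For the decision curve, if the logistic model is fitted in the 1:1 sample, shift its intercept and weight net benefit to the same prevalences, and show treat-all and treat-none alongside.

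The cost is analysis wording only, with no new subjects, samples or assays. The investigators must choose and defend the prevalences, and the reported PPV will be much less favourable.

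### The tumour-type comparison names no test that allows for unequal variances: ordinary ANOVA could run well above 5% if small tumour types vary more, and Welch ANOVA would largely prevent this

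*Protocol*

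**What the plan says.** Protocol section 5.3, Main analysis 1, compares cases with controls. It begins "After Shapiro-Wilk normality and Levene homogeneity of variance tests", and then states that "independent sample t-tests (conforming to normal distribution) or Mann-Whitney U tests (non-normal data) were selected". Both branches turn on normality. Levene is run, but no consequence is written for a significant result, and no Welch test is named. The planned sizes are "500 cases in the case group and 500 cases in the healthy control group".

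Secondary analysis 1 in the same section covers tumour types: "One-way analysis of variance (ANOVA) or Kruskal-Wallis test was used to compare the level differences among different tumor types", with Bonferroni-adjusted post hoc tests. This sentence contains no rule for choosing between the two tests, no variance check and no unequal-variance version.

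Comparing tumour types is a stated secondary objective (section 3.1.2, and Objective 2 in section 2.1.2). The case criteria in section 4.1 admit any cytologically or histologically confirmed malignant solid tumour needing treatment, with no number per type. The only case mix in the document is the pilot list (section 2.1.3, Figure 3).

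**The concern.** Ordinary one-way ANOVA pools the within-group variances, weighting each group by its size. When groups are equal in size, unequal spread does little damage. When sizes and spreads both differ, the F test no longer holds its nominal level. It rejects too often if the small groups are the more variable ones, and too rarely if the large groups are. Kruskal-Wallis is also affected, because a difference in spread alone can move its rejection rate.

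In a pan-tumour study recruited without quotas, some types will probably be common and others rare. The stake is a false claim that the marker differs between tumour types, or a real difference missed. The case-control comparison has near-equal groups and is hardly touched.

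**Working it through.** **1. Inputs from the protocol.** Level 0.05; 500 cases and 500 controls; 10% dropout (all section 5.3). Pilot solid tumours (Figure 3): stomach 7, lung 5, pancreas 5, colon 4, ovary 4, breast 3, liver 3, bile duct 3, cervix 2, prostate 1, oesophagus 1. That is 38; the other 2 of the 40 pilot cases had multiple myeloma. The protocol states no error rate for the tumour-type test, so there is no figure of its own to reproduce.

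**2. Assumptions.** The pilot mix is scaled by 500/38: 7 becomes 92, 5 becomes 66, 4 becomes 53, 3 becomes 39, 2 becomes 26, 1 becomes 13. This gives eleven groups of 92, 66, 66, 53, 53, 39, 39, 39, 26, 13 and 13 (N = 499). Data are normal with equal means. SDs are not in the protocol, so the ratio of largest to smallest is varied.

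**3. Why the level moves.** With equal means the expected mean squares are

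- within: Σ(n_i − 1)σ_i² / (N − k)
- between: Σ(1 − n_i/N)σ_i² / (k − 1)

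Take SD 2 in the three smallest types (26 + 13 + 13 = 52 patients) and SD 1 in the other eight (447 patients):

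- within: (49 × 4 + 439 × 1) / 488 = 635/488 = 1.30
- between: [(3 − 52/499) × 4 + (8 − 447/499) × 1] / 10 = (11.58 + 7.10)/10 = 1.87
- ratio: 1.87/1.30 = 1.44

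The ratio should be 1. With SD 1.5 in place of 2, the same sums give within 549.25/488 = 1.13, between 13.62/10 = 1.36, ratio 1.21. The excess arises with no true difference in means.

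**4. Simulated false-positive rates, nominal 5%, pilot mix scaled to 499.** Most ANOVA and Welch entries rest on 20,000 runs. The 1.25 row (4,000 runs) and the random-pairing column (2,500 runs) rest on fewer. Where a range is shown, the lower value has SDs rising linearly as size falls, and the upper has the larger SD in the three smallest types only.

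| SD ratio | ANOVA, smaller types vary more | ANOVA, spread paired with size at random | ANOVA, larger types vary more | Welch ANOVA |
|---|---|---|---|---|
| 1.25 | about 8% | – | – | about 5% |
| 1.5 | 10.3–13.6% | 5.4% | 2.5% | 5.0–5.3% |
| 2 | 16.7–24.6% | 6.4% | 1.9% | 5.1–5.6% |

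Kruskal-Wallis, with SDs rising linearly as size falls, gives 8.4% at ratio 2 and 12.6% at ratio 3 (500 runs each, so approximate). With random pairing it gives 4.6% (SDs 1 to 1.5) and 5.7% (1 to 2).

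**5. Other case mixes.** With more unequal mixes (for example 200 down to 7 per type) and smaller types more variable, ANOVA gives 15–25% at ratio 1.5 and 26–46% at ratio 2. With ten equal groups of 50 it stays between 5 and 7% up to ratio 3. Welch ANOVA stays at 4.7–5.7% throughout, except 6.0–6.7% in the mix where several types have only 7 to 10 patients.

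**6. Case-control comparison.** Student's t at 500 versus 500 gives 5.0% for SD ratios up to 5. At 500 versus 450, with the smaller group more variable, it gives at most 6.2%; Welch gives 4.9–5.1%. Mann-Whitney at SD 1 versus 2 gives 6.3%.

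**7. Price of Welch.** With equal variances, in a simulation of eight types of 150, 100, 80, 60, 50, 30, 20 and 10 patients, power was 58% with Welch and 61% with ANOVA.

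**The case against.** The strongest reply is that the inflation needs a particular pairing. The protocol gives no type sizes, no SDs and no reason why rarer tumours should be more variable. If spread is unrelated to size, ANOVA averages 5.4–6.4% on the pilot mix, and the opposite pairing makes it conservative. This stands, and it is why the effect is given as a range. It does not remove the problem: the actual pairing will be whatever the recruited sample brings, and a test that holds its level under any of them is available at little cost.

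A second reply is that Welch variants and post hoc tests are detail for a statistical analysis plan, which is not at hand. This carries some weight for the missing Levene consequence. It carries less for tumour types, where the protocol already names the tests and neither holds its level under unequal spread with unequal sizes.

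Stronger readings are tempting but not supported:

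- A reader might infer one headline rate. Eight types of 150 down to 10 patients, with SDs rising from 0.8 to 2.0 as size falls, do give ANOVA about 27–29%. That is neither a bound nor derivable from the protocol; the same sizes and SDs paired at random give 7.3%.
- A reader might carry the normality-only rule over to the tumour types. It is written for the case-control comparison; the tumour-type sentence has no selection rule.
- A reader might conclude that the main result is compromised, or its effect measure unknown until the data are seen. Step 6 shows the level is nearly intact. The AUC and Cohen's d are listed without being tied to either test; only mean versus median difference depends on the branch.
- Dropping every pre-test, making Mann-Whitney primary or analysing logs is partly preference. Nothing in the document shows that logs would stabilise the variance.

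**Conclusion.** The point holds for the tumour-type comparison. Section 5.3 offers only ordinary ANOVA or Kruskal-Wallis, and neither holds its level when group sizes and spreads differ together. Unequal sizes are an inference from open enrolment and the pilot list, though a well-supported one. Unequal spread, and its pairing with small types, is an assumption. On the pilot mix, an SD ratio between 1.25 and 2 with smaller types more variable puts ANOVA at about 8 to 25%. Kruskal-Wallis reduces the inflation without removing it. The Levene test without a consequence is a real gap in the text, but nearly harmless at 500 versus 500. Severity is minor to moderate, confined to a secondary objective.

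**What to change.** In Secondary analysis 1 of section 5.3, name Welch ANOVA as the tumour-type test, with Games-Howell pairwise comparisons in place of the Bonferroni-adjusted post hoc test (Games-Howell carries its own multiplicity adjustment). Set in advance a minimum number of patients per type, below which types are pooled. The check supports a minimum above 10: Welch stayed at 5.0–5.6% on the pilot mix, where the smallest type has 13 patients, but reached 6.7% with several types of 7 to 10.

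In Main analysis 1, state that any t-test is the Welch version. No Levene branch is then needed and the Levene test can be removed.

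The cost is a few lines in section 5.3 and about 3 points of power for the tumour-type test if all variances turn out equal. Pooling also means that very rare types are not compared individually.
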